13.2 Sample Size/Accrual Rate

Our estimated sample size is 20 participants. ALK translocations are identified in approximately 4-5% of patients with NSCLC. At MGH alone, approximately 500 patients with NSCLC undergo genotyping annually. Since a majority of these cases are likely to be ALK TKI naïve our study population is likely to be smaller. Across all participating institutions, we hope to enroll 1 participant per month.

13.3 Analysis of Secondary Endpoints

Secondary endpoints will be analyzed for exploratory purposes only. Participants with ALK TKI resistance and those with ALK TKI intolerance will be analyzed collectively and as distinct cohorts for all endpoints.

Disease Control Rates: Disease control rates (DCR) will be scored according to RECIST version 1.1 criteria and consist of complete response, partial response, and stable disease.

Progression-free and Overall Survival Rates: Progression-free survival (PFS) will be defined as the time from the date of study enrollment to the date of first documented progression or death due to any cause. Overall survival will be defined as the time from study enrollment to death from any cause.

Safety: Toxicity will be assessed using CTC v4.02 criteria. All participants who receive any amount of study drug will be evaluable for toxicity.

KRAS Mutations: Concurrent KRAS mutations will be reported as frequencies. Descriptions of the specific KRAS mutations will also be reported.

ALK Translocation Variant: Exploratory, hypothesis-generating analysis will be performed to correlate different ALK translocation variants with response to treatment with AUY922.

Mechanisms of Resistance: Exploratory, hypothesis-generating analyses will be performed to correlate any findings from the various potential biomarker studies listed in Section 8 with the primary and secondary study endpoints above.

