1.3.1 Secondary Endpoints

- OS, defined as time from study entry to death from any cause.
- PFS, defined as time from study entry to progression or death, whichever comes first.
- DCR, defined as PR, CR, or stable disease (SD) as assessed by RECIST version 1.1.
- Safety parameters: Adverse drug reactions and serious adverse drug reactions, changes in hematology and chemistry values, including those associated with hepatic and renal function, and assessment of physical examination, vital signs, ocular symptoms and cardiac function (i.e. repeated electrocardiograms). CTCAE version 4.02 will be used.
- Mechanisms of treatment resistance: pre- and post-treatment changes in mutational profile of tumor biopsy specimens.

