4. REGISTRATION PROCEDURES

4.1 General Guidelines for DF/HCC and DF/PCC Institutions

Institutions will register eligible participants with the DF/HCC Quality Assurance Office for Clinical Trials (QACT) central registration system. Registration must occur prior to the initiation of therapy. Any participant not registered to the protocol before treatment begins will be considered ineligible and registration will be denied.

A member of the study team will confirm eligibility criteria and complete the protocol-specific eligibility checklist.

Following registration, participants may begin protocol treatment. Issues that would cause treatment delays should be discussed with the Principal Investigator. If a participant does not receive protocol therapy following registration, the participant's protocol status must be changed. Notify the QACT Registrar of participant status changes as soon as possible.

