9.1.5 Duration of Response

Duration of overall response: The duration of overall response is measured from the time measurement criteria are met for CR or PR (whichever is first recorded) until the first date that recurrence or PD is objectively documented, taking as reference for PD the smallest measurements recorded since the treatment started.

Duration of overall complete response: The duration of overall CR is measured from the time measurement criteria are first met for CR until the first date that recurrent disease is objectively documented.

Duration of stable disease: Stable disease is measured from the start of the treatment until the criteria for progression are met, taking as reference the smallest measurements recorded since the treatment started.

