9.1.6 Progression-Free Survival

Progression-Free Survival (PFS) is defined as the duration of time from study enrollment to time of objective disease progression or death from any cause.

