13.4 Reporting and Exclusions

- 13.4.1 **Evaluation of toxicity.** All participants will be evaluable for toxicity from the time of their first treatment.
- 13.4.2 **Evaluation of response.** Participants who received no study treatments will not be evaluated for response to treatment. All other participants included in the study will be assessed for response to treatment, even if there are major protocol treatment deviations or if they are ineligible.

All of the participants who met the eligibility criteria and were enrolled, except participants who did not receive any study medication, will be included in the main analysis of the response rate and calculation of survival.

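### PFS and OS are timed from enrollment in a set limited to participants who reached first dose, so pre-dose deaths cannot count and both endpoints lean upward by a modest, unstated amount

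*Combined protocol and SAP*

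**What the plan says.** **Time origin.** Section 13.3 defines PFS with "Progression-free survival (PFS) will be defined as the time from the date of study enrollment to the date of first documented progression", or death, and adds that "Overall survival will be defined as the time from study enrollment to death from any cause". Section 9.1.6 agrees on PFS: "the duration of time from study enrollment to time of objective disease progression or death from any cause". Section 1.3.1 uses another term for both endpoints, for example "OS, defined as time from study entry to death from any cause". Neither enrollment nor study entry is tied to a specific event such as consent, registration or first dose.

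**Analysis set.** Section 13.4 says that eligible, enrolled participants, "except participants who did not receive any study medication, will be included in the main analysis of the response rate and calculation of survival". The word survival is not split into OS and PFS; I read it as covering both.

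**Order of events.** Section 4.1 requires registration before therapy starts and mentions treatment delays after registration. It also foresees the untreated case ("If a participant does not receive protocol therapy following registration") by asking for a change of status. No maximum interval from registration to first dose is set.

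**Other clocks.** Section 9.1.5 uses a different origin for a related measure: "Stable disease is measured from the start of the treatment until the criteria for progression are met". Best overall response (Section 9.1.4) and the scan calendar (Table 8-1, note 7) also run from the start of treatment.

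**The concern.** The clock starts at one event, and entry to the analysis set depends on a later one. Someone who dies between enrollment and first infusion leaves the analysis. Everyone who is dosed is credited with that interval as survival time. This is the usual setting for immortal-time bias, and it runs upward.

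Estimating OS and PFS is the first secondary objective listed in Section 1.3. With a single arm there is no comparator in which the same shift would cancel. The mixed clocks also mean that a participant with stable disease who then progresses has two durations ending on the same date, a stable-disease duration and a PFS time, which differ by the gap.

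**Working it through.** **Inputs**
- Origin: enrollment or study entry (Sections 1.3.1, 9.1.6, 13.3). Set: dosed participants (Section 13.4). Planned size: 20 (Section 13.2).
- Gap g from enrollment to first dose: not stated, so assumed to be 3, 7, 14 or 21 days. The low end takes enrollment as registration close to dosing. Registration needs a completed eligibility check (Section 4.2), eligibility includes laboratory limits (Section 3.1), and baseline hematology and biochemistry are listed within 72 hours of first infusion (Sections 8.1.8.1, 8.1.8.3). The high end takes enrollment as consent at the start of the 21-day screening window (Section 5, Table 8-1). Neither figure is a stated limit on registration-to-dose time.
- Median from first dose: none is given, so 3, 6 and 12 months are assumed.
- Number enrolled but never dosed, with an event in the gap: not given, so k = 0, 1 or 2 is assumed.

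**Step 1: the plan's own figures.** The plan states none for PFS or OS. Its only operating characteristics are for the primary rule of at least 4 responses in 20. Exact binomial: P(X ≥ 4 | n = 20, p = 0.30) = 0.8929, and P(X ≥ 4 | n = 20, p = 0.10) = 0.1330. These reproduce the stated 89% power and 13% type I error. Neither involves a time origin.

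**Step 2: which events can fall in the gap**
- Death before first dose: the participant received no drug and is excluded. Among those retained, S(t) = 1 for death on [0, g) by rule.
- Progression before first dose, never dosed: excluded.
- Progression documented before first dose, then dosed: retained and counted as an early event. This will be rare, because follow-up scans are scheduled every 6 weeks from the start of treatment, so none falls in the gap.

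**Step 3: effect of the origin in the dosed set.** For each dosed participant, time from enrollment = g + time from first dose. With constant g, median from enrollment = g + median from first dose. Using 30.4375 days per month, the shift is:

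| Gap (days) | Shift (months) | % of 3-month median | % of 6-month median | % of 12-month median |
|---|---|---|---|---|
| 3 | 0.10 | 3.3 | 1.6 | 0.8 |
| 7 | 0.23 | 7.7 | 3.8 | 1.9 |
| 14 | 0.46 | 15.3 | 7.7 | 3.8 |
| 21 | 0.69 | 23.0 | 11.5 | 5.7 |

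**Step 4: effect of the exclusion, keeping enrollment as origin.** Simulation of 20,000 trials: 20 dosed participants with exponential times from first dose, a constant gap, k undosed participants with an event placed uniformly in the gap, and no censoring. Mean sample median in months, dosed only → all enrolled:

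| Assumed median | Gap (days) | k = 1 | k = 2 |
|---|---|---|---|
| 3 months | 3 | 3.21 → 2.99 (−0.22) | 3.21 → 2.80 (−0.41) |
| 3 months | 21 | 3.80 → 3.58 (−0.22) | 3.79 → 3.38 (−0.41) |
| 12 months | 3 | 12.57 → 11.71 (−0.86) | 12.56 → 10.90 (−1.66) |
| 12 months | 21 | 13.15 → 12.29 (−0.86) | 13.16 → 11.51 (−1.65) |

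With k = 0 nothing changes.

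**Step 5: how often an event would fall in the gap.** If the hazard were constant from enrollment, the expected number among 20 is 20 × (1 − exp(−g × ln 2 / m)). At m = 12 months this is 0.11 for 3 days and 0.78 for 21 days. The entry requirement of at least 12 weeks' life expectancy (Section 3.1) should make early deaths rarer than that.

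**The case against.** The best reply has four parts.

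1. **Time from enrollment is a legitimate endpoint.** Adding the gap is simply what the definition does. If everyone enrolled is dosed, nobody is removed and there is no selection. This stands: bias against the all-enrolled result needs at least one never-dosed participant, and the documents give no number. What remains in that case is an origin that does not match the treated set or the treatment-start clocks.
2. **The gap may be only days.** If enrollment means registration, the baseline laboratory window points to about 3 days. This is fair, but the window is tied to dosing rather than registration, laboratory tests can be repeated, and Section 4.1 anticipates delays. The gap is therefore not capped.
3. **Separate measures may have separate origins.** True. The stable-disease clock is supporting evidence of a mismatch, not an error in itself.
4. **Nothing depends on it.** Section 13.3 makes secondary endpoints exploratory. They carry no test, threshold or power, and no external comparison is planned in the documents. This limits the priority, not the validity, of the point.

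A reader might also infer that no PFS event of any kind can occur before dosing, or that anyone who progresses or deteriorates in the gap is dropped. Section 13.4 does not say that: it drops only those who received no study drug.

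**Conclusion.** The mismatch is in the text, and it pushes OS and the death component of PFS upward. For progression the gap is nearly event-free in practice, but not by rule. The size is not in the documents. Under a constant gap of 3 to 21 days, dosed-only medians from enrollment exceed those from first dose by 0.10 to 0.69 months: 3.3% to 23.0% of an assumed 3-month median, 0.8% to 5.7% of a 12-month one. Separately, one or two never-dosed participants with early events would mean that the dosed-only median overstates the all-enrolled one by about 0.2 to 0.4 months at a 3-month median.

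A reader might set a gap of 1 to 3 weeks against the 9.1 weeks reported for the earlier NSCLC study (Section 2.3.3.2) and conclude that PFS is inflated by 11% to 33%. The documents do not support that. The 21-day window bounds screening rather than registration to dose, and 9.1 weeks is a mean duration of drug exposure in a mixed NSCLC population, not a median PFS. Nor does the point reach the main conclusion: the 4-of-20 response rule does not use a time origin. This is a cheap improvement to exploratory endpoints.

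**What to change.** Choose one of two options.

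- **Match the clock to the set (simpler).** In Sections 1.3.1, 9.1.6 and 13.3, define PFS and OS from the date of first AUY922 infusion. This fits the treated set in Section 13.4 and the treatment-start clocks in Section 9.1 and Table 8-1.
- **Match the set to the clock.** Keep enrollment, state which date it is (consent or registration), use one term throughout, and change Section 13.4 so that all registered participants enter the PFS and OS analyses, treated or not. Add a line that never-dosed participants are followed for survival, because the schedules in Sections 5.5 and 5.6 are written around stopping treatment.

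Under either option, report the number registered but never dosed, and preferably the distribution of the enrollment-to-dose interval.

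The first option costs about one sentence in each of three sections and uses dates the trial will already hold. It needs no new procedure, no extra participants and no change to the primary analysis. The downside is that reported medians become slightly shorter.

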13.4 Reporting and Exclusions

- 13.4.1 **Evaluation of toxicity.** All participants will be evaluable for toxicity from the time of their first treatment.
- 13.4.2 **Evaluation of response.** Participants who received no study treatments will not be evaluated for response to treatment. All other participants included in the study will be assessed for response to treatment, even if there are major protocol treatment deviations or if they are ineligible.

All of the participants who met the eligibility criteria and were enrolled, except participants who did not receive any study medication, will be included in the main analysis of the response rate and calculation of survival.

14. PUBLICATION PLAN

It is anticipated that the results of this study will first be reported in abstract form, followed by presentation in a peer-reviewed manuscript.

16. APPENDICES

CONFIDENTIAL

This document is confidential. Do not disclose or use except as authorized.

Page 67 of 69

Appendix A

Excluded Medications

The use of any concomitant medication deemed necessary for the care of the participant is permitted, with the following exceptions.

- Therapeutic doses of warfarin sodium are not permitted (>2 mg/day)
- If, after a participant has enrolled, he/she requires the concomitant use of any of the medications listed in Table 1-1 which may cause QT prolongation, then the participant must be discontinued from the study. Excluded medications which may cause QTc prolongation are also listed and updated in website: qtdrugs.org/medical-pros/drug-list/drug-lists.htm.
- Participants whose cancer has progressed while receiving HSP90 or HDAC inhibitors should be excluded from entering the study.

Table 1-1 List of Excluded Medications

Drug Name	Drug Class	Reason for Exclusion
17-AAG	HSP90 Inhibitor	Known to have HSP90 inhibition
17-DMAG	HSP90 Inhibitor	Known to have HSP90 inhibition
Amitriptyline	Antidepressant	May prolong QTc
Apicidin	Cyclic Peptid	Known to have HDAC inhibition
Arsenic trioxide	Miscellaneous	May prolong QTc
Bepiridil	Miscellaneous	May prolong QTc
CBHA	Hydroxamic Acids	Known to have HDAC inhibition
CGI 242	HSP90 Inhibitor	Known to have HSP90 inhibition
Chloroquine	Anti-malarial	May prolong QTc
Chlorpromazine	Anti-psychotic	May prolong QTc
CI-944	Benzamides	Known to have HDAC inhibition
Cisapride	Miscellaneous	May prolong QTc
CNF 1010	HSP90 Inhibitor	Known to have HSP90 inhibition
Depsipeptide/FK228	Cyclic Peptid	Known to have HDAC inhibition
Desipramine	Antidepressant	May prolong QTc
Dolasetron	Anti-emetic	May prolong QTc
Domperidone	Miscellaneous	May prolong QTc
Doxepin	Antidepressant	May prolong QTc
Droperidol	Miscellaneous	May prolong QTc
Gatifloxacin	Antibiotic	May prolong QTc
Halofantrine	Anti-malarial	May prolong QTc
Imipramine	Antidepressant	May prolong QTc
IPI-504	HSP90 Inhibitor	Known to have HSP90 inhibition
Itraconazole	Antifungal	May prolong QTc and CYP3A4 inhibitor
Ketoconazole	Antifungal	May prolong QTc and CYP3A4 inhibitor
KOS-953	HSP90 Inhibitor	Known to have HSP90 inhibition
LAQ824	Hydroxamic Acids	Known to have HDAC inhibition
Maprotiline	Antidepressant	May prolong QTc
Mesoridazine	Anti-psychotic	May prolong QTc
Methadone	Miscellaneous	May prolong QTc
Moxifloxacin	Antibiotic	May prolong QTc
MS-275	Benzamides	Known to have HDAC inhibition
Ondansetron	Anti-emetic	May prolong QTc

CONFIDENTIAL

This document is confidential. Do not disclose or use except as authorized.

Pentamidine	Miscellaneous	May prolong QTc
Pimozide	Anti-psychotic	May prolong QTc
Risperidone	Anti-psychotic	May prolong QTc
SAHA	Hydroxamic Acids	Known to have HDAC inhibition
Sodium butyrate	Hydroxamic Acids	Known to have HDAC inhibition
Sparfloxacin	Antibiotic	May prolong QTc
SRN 005	HSP90 Inhibitor	Known to have HSP90 inhibition
Stresgenin B	HSP90 Inhibitor	Known to have HSP90 inhibition
Thioridazine	Anti-psychotic	May prolong QTc
Tropisetron	Anti-emetic	May prolong QTc
TSA	Hydroxamic Acids	Known to have HDAC inhibition
Venlafaxine	Antidepressant	May prolong QTc
Ziprasidone	Anti-psychotic	May prolong QTc

Medications to be Used with Caution

The *in vitro* metabolism studies suggest that AUY922 is a moderate inhibitor of CYPs 2C8, 2C9, 2C19, and 3A4. Therefore, drugs known to be metabolized by or act as inducers or inhibitors of CYPs 2C8, 2C9, 2C19, and 3A4 should be used caution because of the risk of either reduced or enhanced activity / toxicity of the respective concomitant medication.

Participants using concomitant medications known to be metabolized by these CYP isoenzymes or to interact with these enzymes will not be excluded from the study; however, the participants must be carefully monitored for potentiation of toxicity. For an up to date list of concomitant medications that are metabolized by or act as inducers/inhibitors of CYPs 2C8, 2C9, 2C19 and 3A4, please see:

<http://medicine.lupui.edu/clinpharm/ddis/table.aspx>
